8.3.4 TIME PERIOD AND FREQUENCY FOR EVENT ASSESSMENT AND FOLLOW-UP

The occurrence of an AE or SAE may come to the attention of study personnel during study visits, during interviews of a study participant presenting for medical care, or upon review by a study monitor. All AEs including local and systemic reactions not meeting the criteria for SAEs will be captured on the appropriate report form. Information to be collected includes event description, time of onset, clinician's assessment of severity, relationship to study product (assessed only by

those with the training and authority to make a diagnosis), and time of resolution/stabilization of the event. All AEs occurring while on study must be documented appropriately regardless of relationship. All AEs will be followed to adequate resolution.

A SAE follow-up includes a prompt blood sampling for PK analyses, if deemed applicable by the Investigator or by his/her staff. Any medical condition that is present at the time that the study participant is screened will be considered as baseline and not reported as an AE. However, if the study participant's condition deteriorates while performing any physical assessments at any time after signing the ICF (including the screening period), it will be recorded as an AE. Unanticipated problems (UPs) will be recorded in the data collection system throughout the study.

Changes in the severity of an AE will be documented to allow an assessment of the duration of the event at each level of severity. AEs characterized as intermittent require documentation of onset and duration of each episode.

The PI will record all reportable events with start dates occurring any time after informed consent is obtained until the last day of study participation. At each study visit, the investigator will inquire about the occurrence of AEs/SAEs since the last visit. Events will be followed for outcome information until resolution or stabilization.

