2.3 RISK/BENEFIT ASSESSMENT

2.3.1 KNOWN POTENTIAL RISKS

Potential risks are related to the long-term administration of an investigational drug to participants suffering from multiple chronic diseases.

BIO101 was well tolerated in healthy elderly volunteers receiving up to 450 mg b.i.d. for 14 days. Based on non-clinical safety (26-week studies **example 1**, safety pharmacology and phase 1 results, both immediate and long-ranging risks can be considered as low.

The active ingredient in BIO101, 20E, may become a restricted substance, which is not allowed to be used in sport competitions. The reason is that there is a tendency to use it as an anabolic agent. Since BIO101 contains a high concentration of 20E at a dose that is much higher than the one that appears in nutritional supplements, there is concern that non-sarcopenic individuals may want to use BIO101 illicitly. Participants in this study will be warned and instructed to not allow anyone to gain access to their medication and to use only according to the medication instructions provided in the drug kits.

In addition,

putative mechanism of action through activation of the MAS receptor and potential impact on the renin–angiotensin–aldosterone system (RAS) requires attention. A special surveillance and precaution will be taken with events that could theoretically indicate presence of orthostatic hypotension (OTH), including dizziness and presyncope related to orthostatic changes and actual measurements. In addition, events that comply with the clinical definition of OTH (i.e. decrease in systolic blood pressure of 20 mm Hg or a decrease in diastolic blood pressure of 10 mm Hg within three minutes of standing when compared with blood pressure from the sitting or supine position) will require special attention even without symptoms.

There are limited risks linked to the execution of the functional tests, e.g. falling during a test. The investigational site staff will put in place adapted surveillance, adequate prevention including cancellation or postponing of a planned test, and adapted emergency care in order to prevent, limit and appropriately and timely treat possible adverse events.

All AEs will be reported as per standard pharmacovigilance procedures (Section 8.4).

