7 STUDY INTERVENTION DISCONTINUATION AND PARTICIPANT DISCONTINUATION/WITHDRAWAL

7.1 DISCONTINUATION OF STUDY INTERVENTION

The Investigator should discontinue study intervention and specifically ensure that a participant stops taking the investigational drug if the bioanalytical results at Month 1 or Month 3 shows the following changes:

1. Confirmed 3-fold or greater elevations above the Upper Limits of Normal (ULN) of

These stopping rules for discontinuation are established based on

Discontinuation from investigational oral treatment does not mean discontinuation from the study, and remaining study procedures should be completed as indicated by the study protocol. If a clinically significant finding is identified (including, but not limited to, changes from baseline) after enrollment, the investigator or qualified designee will determine if any change in participant management is needed. Any new clinically relevant finding will be reported as an AE.

The data to be collected at the time of study intervention discontinuation will include the following:

- AE complete follow-up (if the treatment is stopped following an AE)
- Last investigational medication administration date and time

The physician can decide to re-introduce the investigational treatment if it was stopped because of a concomitant acute condition he/she considers unrelated to the treatment.

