- Assessment of AEs: At each visit, participants will be explicitly asked to report any new symptoms or any newly observed abnormality since the previous study visit. An unsolicited AE is one reported without any prompting or in response to a general question such as "Have you noticed anything different since you started the study, since you began the study intervention and etc.". A solicited AE is one that is specifically solicited such as "Have you noticed any falls since you started the study medication?". Ongoing AEs/SAEs will be followed up until resolution or clinical stabilization. See also Section 8.3.4, Time Period and Frequency for Event Assessment and Follow-Up.

Participants will be provided with the results of their ECG and laboratory analyses.

Due to the COVID-19 situation and safety concerns over viral transmission, every investigational visit within the protocol is now be performed remotely (e.g. by phone) for all participants still active in the study by the investigational site staff. The investigational site will continue to monitor the health status of the participants by collecting information on general health status, Concomitant Medication and Adverse Events.

M7.5 and M10.5 phone calls include a pre-diabetic questionnaire as recommended by

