8.3 ADVERSE EVENTS AND SERIOUS ADVERSE EVENTS

8.3.1 DEFINITION OF ADVERSE EVENTS (AE)

An adverse event means any untoward medical occurrence associated with the use of an intervention in humans, whether or not considered intervention-related (21 CFR 312.32 (a)).

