8.3.6 SERIOUS ADVERSE EVENT REPORTING

The study clinician will immediately report to the sponsor of any SAEs, whether or not considered study intervention related, including those listed in the protocol or investigator brochure, and must include an assessment of whether there is a reasonable possibility that the study intervention caused the event. Study endpoints that are SAEs (e.g. all-cause mortality) must be reported in accordance with the protocol unless there is evidence suggesting a causal relationship between the study intervention and the event (e.g. death from anaphylaxis). In that case, the investigator must immediately report the event to the sponsor.

All SAEs will be followed until satisfactory resolution or until the site investigator deems the event to be chronic or the participant is stable. Other supporting documentation of the event may be requested by the Data Coordinating Center (DCC)/study sponsor and should be provided as soon as possible.

The study sponsor will be responsible for notifying the FDA of any unexpected fatal or lifethreatening suspected adverse reaction as soon as possible, but in no case later than 7 calendar days after the sponsor's initial receipt of the information. In addition, the sponsor must notify the FDA and all participating investigators in an Investigational New Drug (IND) safety report of potential serious risks, from clinical trials or any other source, as soon as possible, but in no case later than 15 calendar days after the sponsor determines that the information qualifies for reporting.

Follow-up information on SAEs must also be reported by the investigator within the same time frames.

If a non-serious AE becomes serious, this and other relevant follow-up information must also be provided to within one day as described above. For a non-serious AE that becomes serious but which is not fatal or life-threatening, a complete clinical report should be received within 5 days.

The following variables will be recorded for each AE: verbatim AE description, time and date for AE start and stop, maximum intensity, seriousness, causality rating, whether or not the AE caused the patient to discontinue, and the outcome.

All SAEs have to be reported, whether or not considered causally related to the study procedures. All SAEs will be recorded in the eCRF. The investigator is responsible for informing the IEC/IRB of the SAE based on local requirements.

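### Protocol 8.3.4 excludes conditions present at screening from AE recording unless they deteriorate during a study assessment, so non-serious worsening elsewhere may go unrecorded or be recorded inconsistently

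*Protocol*

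**What the plan says.** Protocol 8.3.4 holds the only rule on conditions a participant already has. A condition "present at the time that the study participant is screened will be considered as baseline and not reported as an AE". The next sentence, introduced as a contrast, provides that an AE will be recorded if the participant's "condition deteriorates while performing any physical assessments at any time after signing the ICF"; it adds that the screening period is included.

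Other sections bear on the same question:

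- **Protocol 8.3.1** defines an AE as "any untoward medical occurrence associated with the use of an intervention in humans, whether or not considered intervention-related".
- **Protocol 7.1** has two adjacent sentences. One begins "If a clinically significant finding is identified (including, but not limited to, changes from baseline) after enrollment" and leaves it to the investigator whether the participant's management should change. The other reads "Any new clinically relevant finding will be reported as an AE".
- **Protocol 8.2** says that at each visit "participants will be explicitly asked to report any new symptoms or any newly observed abnormality since the previous study visit". It also gives an open question, whether the participant has noticed anything different, as an example of how an unsolicited AE comes to light.
- **Protocol 8.3.6** states "All SAEs have to be reported, whether or not considered causally related to the study procedures".
- **Protocol 2.3.1** opens its account of risk with "Potential risks are related to the long-term administration of an investigational drug to participants suffering from multiple chronic diseases".
- **SAP 8.8.1** classes an AE as treatment-emergent if it starts between the first dose and six weeks after the last dose. Pre-treatment AEs appear in listings only.

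**The concern.** The rule in 8.3.4 depends on where a worsening takes place. A known disease that worsens during a walk test is an AE; the same disease worsening equally at home is not clearly one. Setting says nothing about whether the drug contributed, so it is a poor basis for what enters the safety tables.

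The population makes this matter. The protocol itself places the risk in long-term dosing of people with several chronic diseases, and eligibility admits many of them. Section 5.3 excludes severe arthritis and NYHA class III or IV heart failure, and temporarily excludes blood pressure above 200 systolic or 110 diastolic and uncontrolled diabetes. Milder forms of all these can enter. For such participants a harmful drug effect could well take the form of an existing condition getting worse.

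AE counts by arm are a main safety result of the trial. If sites follow the literal text, those counts are understated; if some follow it and others apply the broader definition, they are inconsistent.

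**Working it through.** The plan states no figure on this point and no arithmetic applies. The check takes one case and follows it through each provision. Suppose a participant enters with non-severe arthritis, which eligibility allows, and during treatment it worsens without meeting any seriousness criterion: (a) during the 400-metre walk test, or (b) at home.

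1. **8.3.4, baseline rule.** The arthritis was present at screening, so it is baseline in both cases.
2. **8.3.4, exception.** Case (a) meets it and is recorded. Case (b) does not. The section does not say that home worsening is excluded; that follows from a general exclusion with a single stated exception.
3. **8.3.4, remaining text.** The investigator records reportable events whose start date falls after consent. The arthritis began before consent, and nothing makes the date of worsening a new start date. The instruction to document changes in severity concerns something already classed as an AE.
4. **8.3.1.** The definition is wide enough to include case (b) but does not mention worsening. Against it stands a more specific rule in 8.3.4, and a site may reasonably follow the specific rule.
5. **7.1.** Case (b) may be a change from baseline and so a clinically significant finding. But that sentence governs participant management. The sentence that requires AE reporting is limited to a new clinically relevant finding, and whether a flare of known arthritis is new is left to the reader.
6. **8.2.** The visit question asks about new symptoms and newly observed abnormalities. The open example could bring case (b) to light, but classification then returns to 8.3.4.
7. **8.3.6.** All serious events are reported, with no exception for existing disease. Case (b) is not serious. Even a serious worsening must first be an AE, because 8.3.2 defines a serious event as an AE with certain outcomes.
8. **SAP 8.8.1.** The definition works on start date alone and has no clause for worsening on treatment. An event never recorded as an AE cannot enter. An AE that starts between consent and first dose and then worsens on treatment keeps its early start date and stays in the listings. Protocol 8.3.5 likewise leaves AEs before randomization out of the analysis.

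Case (a) is therefore an AE by express rule. Case (b) is an AE only if the site prefers 8.3.1, or a generous reading of 7.1, to 8.3.4.

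**COVID-19 schedule.** Under Protocol 1.3 the M1, M3 and M6 visits became telephone calls. The physical examination, vital signs and functional tests are marked at baseline or screening and again at the end-of-intervention visit, with none in between. For participants on that schedule the exception could rarely apply in the interval. Participants who finished earlier had on-site visits and are not affected in this way.

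**The case against.** The strongest reply is that 8.3.4 nowhere says that worsening at home is not an AE. It gives one case that will be recorded and does not call it the only one. The reference to the screening period suggests that the sentence was meant to clarify deterioration during tests, not to close other routes. The same section asks for all AEs on study to be documented whatever their relationship to treatment, and names interviews during medical care and monitor review as sources. With 8.3.1, the change-from-baseline wording in 7.1, the open question in 8.2 and the safety questions and AE review at the scheduled calls, a careful investigator has several ways to record such an event. This stands to the extent that a reader might infer that home worsening is never an AE; the documents do not support that.

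A reader might also infer that a drug effect on blood pressure or glucose would be lost to analysis. The documents do not support that either. Orthostatic hypotension is an event of special interest and is tabulated separately. Blood pressure is summarized by position as change from baseline (SAP 8.8.3). Glucose and HbA1c are summarized as change from baseline with shift tables (SAP 8.8.2). Diabetes questions are asked at M7.5 and M10.5, and treatment started for a worsening disease appears in the concomitant medication summaries (SAP 8.5.4). The revised schedule makes some of these measurements less frequent but keeps the end-of-intervention assessment.

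Finally, a reader might multiply the 77 participants per arm by a guessed rate of worsening. No such rate is given, and the product would also assume that every worsening escapes every other route.

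What the reply does not remove is the conflict itself. No provision expressly makes worsening of an existing condition an AE, and the one section that addresses existing conditions points the other way.

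**Conclusion.** The point holds as a defect in a recording rule. The exception in 8.3.4 is too narrow, it is at odds with 8.3.1, and it sits poorly with 7.1 and with the protocol's own account of risk. The SAP does not correct it. The consequence is that non-serious worsening of existing disease outside a study assessment may be left out of the AE tables, or recorded at one site and not at another.

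The size cannot be estimated. The documents give neither a rate of worsening nor any indication of how sites read the rule. The conclusion rests on a literal reading of 8.3.4 and on the assumption that at least some sites follow the specific rule over the general definition. It is limited to AE counts; effects on measured variables and the event of special interest would still be visible in part. The correction is worth making because it changes which events are counted by arm and costs little.

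**What to change.** Three changes, all to recording and classification and none to clinical management:

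1. **Protocol 8.3.4.** Replace the exception with a rule such as: *if a pre-existing condition worsens in severity or frequency at any time after consent, whether or not during a study assessment, it is recorded as an AE with the date of worsening as its onset.*
2. **Protocol 8.2.** Add *or any worsening of an existing condition* to what participants are asked at visits and on calls, and carry this into the site question script.
3. **SAP 8.8.1.** State that a pre-existing condition or a pre-treatment AE that worsens on or after the first dose counts as treatment-emergent. Change 1 already gives a worsened pre-existing condition a new onset date; this clause is needed chiefly for AEs that begin between consent and first dose.

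The cost is a few sentences and somewhat more AEs to record in all arms. The change to recording works forward only; earlier worsening would be recovered only as far as source records allow.

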8.3.5 ADVERSE EVENT REPORTING

For the purposes of this study, AEs will be recorded from the time of informed consent until the completion of the study or at the end-of-study visit. However, AEs occurring prior to randomization will not be included in the analysis of the reports of events so it will not be part of the risk-benefit assessment in relation to the study intervention.

All ongoing AEs should be followed up for 30 days after the end-of-study visit.

8.3.6 SERIOUS ADVERSE EVENT REPORTING

The study clinician will immediately report to the sponsor of any SAEs, whether or not considered study intervention related, including those listed in the protocol or investigator brochure, and must include an assessment of whether there is a reasonable possibility that the study intervention caused the event. Study endpoints that are SAEs (e.g. all-cause mortality) must be reported in accordance with the protocol unless there is evidence suggesting a causal relationship between the study intervention and the event (e.g. death from anaphylaxis). In that case, the investigator must immediately report the event to the sponsor.

All SAEs will be followed until satisfactory resolution or until the site investigator deems the event to be chronic or the participant is stable. Other supporting documentation of the event may be requested by the Data Coordinating Center (DCC)/study sponsor and should be provided as soon as possible.

The study sponsor will be responsible for notifying the FDA of any unexpected fatal or lifethreatening suspected adverse reaction as soon as possible, but in no case later than 7 calendar days after the sponsor's initial receipt of the information. In addition, the sponsor must notify the FDA and all participating investigators in an Investigational New Drug (IND) safety report of potential serious risks, from clinical trials or any other source, as soon as possible, but in no case later than 15 calendar days after the sponsor determines that the information qualifies for reporting.

Follow-up information on SAEs must also be reported by the investigator within the same time frames.

If a non-serious AE becomes serious, this and other relevant follow-up information must also be provided to within one day as described above. For a non-serious AE that becomes serious but which is not fatal or life-threatening, a complete clinical report should be received within 5 days.

The following variables will be recorded for each AE: verbatim AE description, time and date for AE start and stop, maximum intensity, seriousness, causality rating, whether or not the AE caused the patient to discontinue, and the outcome.

All SAEs have to be reported, whether or not considered causally related to the study procedures. All SAEs will be recorded in the eCRF. The investigator is responsible for informing the IEC/IRB of the SAE based on local requirements.

8.3.7 REPORTING EVENTS TO PARTICIPANTS

Not applicable

8.3.8 EVENTS OF SPECIAL INTEREST

In this study, falls and injurious falls as well as orthostatic hypotension are considered events of special interest.

8.3.9 REPORTING OF PREGNANCY

Not applicable
8.4 UNANTICIPATED PROBLEMS

8.4.1 DEFINITION OF UNANTICIPATED PROBLEMS (UP)

The Office for Human Research Protections (OHRP) considers unanticipated problems involving risks to participants or others to include, in general, any incident, experience, or outcome that meets all of the following criteria:

Unexpected in terms of nature, severity, or frequency given:

- The research procedures that are described in the protocol-related documents, such as the IEC/IRB-approved research protocol and informed consent document
- The characteristics of the participant population being studied
- The event is related or possibly related to participation in the research ("possibly related" means there is a reasonable possibility that the incident, experience, or outcome may have been caused by the procedures involved in the research)
- The suggestion that the research places participants or others at a greater risk of harm (including physical, psychological, economic, or social harm) than was previously known or recognized

This study will use the OHRP definition of UP.

In this study, in which tests an investigational drug in older adults, and applies well established diagnostic tests and procedures, all precautions will be taken for prompt detection and reporting of UPs.

